6.5 Concomitant Therapies

All treatments and therapies used 30 days prior to enrollment and all treatments or therapies used during the course of the study must be recorded in the Case Report Form (CRF) or electronic Case Report Form (eCRF).

6.5.1. Authorized Therapies

Prescription treatments for plaque psoriasis, including biologics, oral or topical therapy for psoriasis, and UV therapy, are required for this study.

Protocol Version 02: 29 January 2024

This document contains confidential, proprietary information.

Protocol GLI.04.US.SL.035

CONFIDENTIAL

Unless listed under the exclusion criteria (see Section 6.4) or in Prohibited Therapies (see Section 6.5.2), other therapies to treat ongoing conditions are authorized.

6.5.2. Prohibited Therapies

None other than as specified in the Inclusion/Exclusion criteria.

The decision to administer a prohibited medication/treatment should be made with the safety of the subject being the primary consideration. Whenever possible, Galderma Laboratories, L.P. should be notified before the prohibited medication/treatment is administered to discuss possible alternatives.

If a subject receives prohibited therapy during the study, the subject may be allowed (at the discretion of the Investigator / Galderma Laboratories, L.P.) to continue in the study for safety evaluation purposes, only.

7. STUDY TREATMENT

The term “study treatment” refers to the study products (see Section 7.1).

7.1 Study Product Identification and Use

Study product: Cetaphil® Gentle Skin Cleanser	
Form	Gel
Mode of administration	Topical
How supplied	Bottle
Formula number	L2-2688A.1 (1747)
Lot number	To be added upon study completion
Storage and handling	Store at room temperate conditions: 15°C to 25°C (or 59°F to 77°F), away from sunlight

Study product: Cetaphil® Moisturizing Cream	
Form	Cream
Mode of administration	Topical
How supplied	Jar and bottle
Formula number	L2-2299A.1 (1765)
Lot number	To be added upon study completion
Storage and handling	Store at room temperate conditions: 15°C to 25°C (or 59°F to 77°F), away from sunlight

Supporting product: Cetaphil® Daily Facial Moisturizer SPF 35	
Form	Lotion

Protocol Version 02: 29 January 2024

This document contains confidential, proprietary information.

Protocol GLI.04.US.SL.035

CONFIDENTIAL

Mode of administration	Topical
How supplied	Bottle
Formula number	217-19229-42 (1727)
Lot number	To be added upon study completion
Storage and handling	Store at room temperate conditions: 15°C to 25°C (or 59°F to 77°F), away from sunlight

The ingredient lists for the study products can be found in Appendix I.

7.2 Additional Products and Materials

The Sponsor will provide study products and supporting products to be used by subjects during the study. The Sponsor will not provide any prescription treatment for plaque psoriasis. The study overhead will cover any additional materials or supplies.

7.3 Study Product Accountability

Upon receipt of the study products, the Investigator or designee will conduct an inventory. In accordance with federal regulations, the Investigator must agree to keep all test article in a secure location with restricted access. Designated study personnel will provide the test article to the subjects in accordance with the protocol.

During the study, the Investigator must maintain records of study treatment dispensation and collection for each subject. This record must be made available to the study monitor for the purposes of verifying the accounting of clinical supplies. Any discrepancies and/or deficiencies between the observed disposition and the written account must be recorded along with an explanation. At the conclusion of the study, the Investigator will be responsible for returning all unused study products (i.e., Cetaphil® products) unless otherwise instructed by the Sponsor. Shipping label and cost will be provided to the Investigator by the Sponsor.

7.4 Study Product Preparation

All study products will be blinded and relabeled as below:

Study Product	Relabel
Cetaphil® Gentle Skin Cleanser	Product name: Cleanser Formula number: 1747 Lot number: xxx Storage conditions: 59°F - 77°F For Clinical Trial Purposes Only
Cetaphil® Moisturizing Cream	Product name: Moisturizer Formula number: 1765 Lot number: xxx Storage conditions: 59°F - 77°F For Clinical Trial Purposes Only

Protocol Version 02: 29 January 2024

This document contains confidential, proprietary information.

Protocol GLI.04.US.SL.035

CONFIDENTIAL

Cetaphil® DFM SPF 35	Product name: Sunscreen SPF 35 Formula number: 1727 Lot number: xxx Storage conditions: 59°F - 77°F For Clinical Trial Purposes Only
----------------------	--

7.5 Treatment Product Dispensing

All treatment products, except the prescription treatment for psoriasis, will be administered only to subjects enrolled in the study, at no cost to subjects, and in accordance with the conditions specified in the protocol.

7.6 Treatments Compliance

Subjects will complete a daily diary, recording treatment product applications and comment during the study. Treatment products and diary will be dispensed at each study visit and reviewed for compliance at the subsequent visits. Treatment products will be visually inspected and weighed prior to distribution at each visit. If subjects do not return the treatment products and daily diary at the study visits, a verbal confirmation will be obtained for usage compliance.

Any suspected noncompliance with the treatment product or study instructions will be addressed by the Investigator or clinic staff. The Investigator will determine whether a subject's noncompliance will affect the study outcome and whether the data should be excluded from statistical analyses.

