9.2 Discontinued Subjects

Any subject is free to discontinue his/her participation in this study at any time and for whatever reason, specified or unspecified, and without prejudice.

An Investigator may decide to discontinue a subject from the study for safety reasons or when it is in the best interest of the subject. Galderma Laboratories, L.P. may also decide to prematurely terminate or suspend the study or the participation of a subject in the study. All data gathered on the subject prior to termination should be made available to Galderma Laboratories, L.P.

Criteria for the discontinuation of a subject during the study will include the following:

- Adverse Event
- Lack of Effect
- Pregnancy
- Subject Request
- Protocol Violation
- Lost to Follow-up
- Any unmanageable factor, in the Investigator's opinion, that may significantly interfere with the protocol or interpretation of results.

Protocol Version 02: 29 January 2024

This document contains confidential, proprietary information.

Protocol GLI.04.US.SL.035

CONFIDENTIAL

The reason and date for withdrawal should be documented in the subject's source documents and CRFs. When possible, an explanatory comment should be added to further explain the reason for the withdrawal. If withdrawal of a subject occurs during a regular study visit, the CRF for that specific visit shall be completed as far as possible.

If a subject is withdrawn from the study, all data collected until the time of withdrawal will be used in the analyses. Subjects who receive study products and are withdrawn or discontinued from the study will not be replaced. For AEs still ongoing at the time of withdrawal, see Section 11.

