12.2 Analysis Population

The following populations will be defined:

Intention-to-treat (ITT)	Includes all subjects who receive the test products, i.e., at least one follow-up visit completion. Subjects are analyzed based on the as treated principle.
Per protocol (PP)	Includes all subjects in ITT who complete the study without any deviations that are considered to have substantial impact on the primary effectiveness outcome.

ITT is the primary population for all efficacy and safety analyses. The primary efficacy analysis will be repeated using the PP analysis set if there is at least a 10% difference in the number of subjects between the PP and ITT sets.

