Questionnaires will be tabulated; and the frequency and percentage of all response options will be reported for each question and time point. For questionnaire inquiries without baseline response data, a binomial (sign) test will be performed to test if the proportion of the combined designated favorable responses is equal to the combined designated unfavorable responses for each applicable question. A higher percentage of favorable responses with a significant *p* value indicates positive subject perceptions of the study treatment.

A more appropriate analysis may be performed, which will be recorded in biostatistics note to file and/or in the study report.

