14.6 Changes in Study Conduct/Amendments

No amendment will be done for modification(s) due to change in logistical or administrative aspect of the study (e.g., change in monitors, change of telephone numbers). In such a case, the appropriate institution(s) and/or person(s) will be notified of the changes.

Protocol Version 02: 29 January 2024

This document contains confidential, proprietary information.

Protocol GLI.04.US.SL.035

CONFIDENTIAL

Modification of the protocol is prohibited without prior written agreement in the form of a protocol amendment. All amendments will be created by Galderma Laboratories, L.P. and must be approved by the IRB prior to implementation except when required to mitigate immediate safety risks or when the changes involve only logistical or administrative revisions.

Amendments may necessitate that the informed consent and other study-related material be revised. If the consent form is revised, all Subjects/subjects currently enrolled in the study may be required by the IRB to sign the approved, revised informed consent form.

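### Section 7.6 lets the open-label Investigator exclude noncompliant subjects' data without confining this to the per-protocol set, in conflict with the ITT rule in Section 12.2

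*Combined protocol and SAP*

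**What the plan says.** Section 7.6 (Treatments Compliance) has compliance checked by diary, inspection and weighing, or by verbal confirmation when products and diary are not returned. It then gives the decision on suspected noncompliance to the Investigator: "The Investigator will determine whether a subject's noncompliance will affect the study outcome and whether the data should be excluded from statistical analyses".

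Section 12.2 (Analysis Population) defines two sets.
- ITT: "Includes all subjects who receive the test products, i.e., at least one follow-up visit completion". Compliance is not a condition.
- PP: "Includes all subjects in ITT who complete the study without any deviations that are considered to have substantial impact on the primary effectiveness outcome".

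It continues: "ITT is the primary population for all efficacy and safety analyses". The primary efficacy analysis is repeated in PP only "if there is at least a 10% difference in the number of subjects between the PP and ITT sets".

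Section 9.2 (Discontinued Subjects) says that for a subject who is withdrawn, "all data collected until the time of withdrawal will be used in the analyses". The discontinuation reasons listed there include lack of effect and protocol violation.

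Section 12.4 (Statistical Analysis Plan) closes with: "A more appropriate analysis may be performed, which will be recorded in biostatistics note to file and/or in the study report".

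**The concern.** The study is open-label. Under Sections 10.1 and 11.1 the Investigator grades BSA, TLSS, PGA and dryness. Section 11.2 also has the Investigator review changes from baseline and questionnaire answers. The relabelling in Section 7.4 hides product names, not outcomes. The role that decides on exclusion can therefore know how a subject has done, and the protocol sets no compliance threshold, no deadline and no independent check.

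Two results are exposed. For efficacy, the test is whether the mean change from Baseline is a decrease, so losing poor responders makes a significant decrease easier to reach. For tolerability, which is part of the primary objective, success under Section 4.2 and Table 5 includes the mere absence of a significant increase. A subject who uses less product because it burns could be called noncompliant and leave that comparison.

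**Working it through.** **1. The passages side by side.** Take a noncompliant subject who received product and completed Week 2.
- Section 12.2: in the ITT set, so in every primary efficacy and safety analysis; possibly out of PP.
- Section 7.6: may be excluded from the statistical analyses, with no set named.
- Section 9.2: if the subject withdraws, the data collected up to then are used. If the subject stays, this sentence does not apply.

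A noncompliant subject who withdraws is therefore kept, while one who stays may be removed. Sections 7.6 and 12.2 cannot both be followed as written.

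**2. The PP comparison as a safeguard.** The trigger is a difference of at least 10%.
- Removed from PP only: 3 of 40 is 3/40 = 7.5% and 4 of 50 is 4/50 = 8%, both below the trigger.
- Removed from ITT itself: if 4 of 50 are dropped, ITT is 46 and PP is at most 46. Those 4 contribute 46 − 46 = 0 to the difference, so the trigger cannot detect them.

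**3. Size.** The protocol gives no SD, effect size or power, so there is no figure to reproduce.

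Inputs from the protocol: N = 50 (the upper end of 40 to 50 completers, Section 6.1), a one-sample t-test of mean change against zero (Section 12.4, Table 5), and a two-sided 5% level (Section 12.1).

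Assumptions: changes d are normal with mean 0 and SD 1, positive meaning worse; k = 3 or 5 subjects are excluded.

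Test on the m = N − k who remain: T = mean(d) / (s/√m). A false decrease is declared if T < −t(0.975, m − 1). The critical value is 2.013 for m = 47 and 2.015 for m = 45.

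Selection: each subject has an index L = ρd + √(1 − ρ²)e, with e independent standard normal. The k largest L are excluded, so ρ is the correlation of exclusion with poor outcome.

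Results from 400,000 simulated trials per row (shift in mean change; chance of a false significant decrease):

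| Exclusion process | k = 3 | k = 5 |
|---|---|---|
| Unrelated to outcome | 0 SD; 2.5% | 0 SD; 2.5% |
| ρ = 0.3 | −0.04 SD; 4.5% | −0.06 SD; 5.9% |
| ρ = 0.5 | −0.06 SD; 6.5% | −0.09 SD; 10.0% |
| Exactly the worst k | −0.12 SD; 17% | −0.19 SD; 33% |
| ρ = −0.3 (good responders) | +0.04 SD; 1.4% | +0.06 SD; 1.0% |
| ρ = −0.5 (good responders) | +0.06 SD; 1.0% | +0.09 SD; 0.6% |

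With nobody excluded the chance is 2.5%. At N = 40, removing exactly the worst 3 gives 19%.

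**The case against.** **Section 7.6 may have been meant for PP only.** Its test, whether noncompliance affects the study outcome, is close to the PP criterion in Section 12.2, so the fault may be a missing cross-reference. That is plausible, but the text does not say it, and supplying that limit is the remedy proposed here.

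**Bias toward benefit is not established.** A reader might infer that the rule will favour the products. No section shows that poor responders are the ones who become noncompliant. All subjects are on or starting prescription therapy, and improved subjects might equally stop moisturizing, which would reverse the direction. This stands: the rule creates a risk, not a demonstrated bias.

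**Grader and decider may differ.** The definition of Investigator in the list of abbreviations includes sub-investigators. Each site also has only 20 to 25 subjects, so nobody is shown to rank all 50. Removal of exactly the worst few is therefore a bound, not a forecast.

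**A clear effect would survive.** If the true decrease were 0.6 SD (assumed), significance would be reached in 98.7% of trials with no removals and 99.9% with the worst 3 removed. The exposure matters when the true change is small.

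**Section 9.2 covers withdrawn subjects only.** It does not directly contradict Section 7.6. What remains is the unequal handling shown above.

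**Section 12.4 and Section 14.6.** A reader might see a contradiction with the amendment rule, "Modification of the protocol is prohibited without prior written agreement in the form of a protocol amendment". But the permission in Section 12.4 is itself protocol text, so using it is not clearly a modification of the protocol. Nor does it say that the planned analysis will be replaced, or that the choice follows sight of the data. The weakness is narrower: it sets no timing and does not require the planned result to be reported.

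**Conclusion.** The point holds as a conflict between Sections 7.6 and 12.2. Section 7.6 states an open-ended exclusion rule, held by a role that grades the outcomes unmasked, and it reaches analyses that Section 12.2 assigns to a set without a compliance condition. The conflict touches every analysis under the primary objective and should be settled before database lock.

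The statistical consequence is conditional. With N = 50 and no true change, excluding 3 to 5 subjects by a process correlated 0.3 to 0.5 with poor outcome puts the false-decrease chance at about 4.5% to 10%, against 2.5%. The 17% and 33% figures are upper bounds. The number excluded, the correlation and the normal model are assumptions. The most plausible direction is toward benefit and apparent tolerability, because the decision-maker may know the outcome, but the documents support only that the rule can bias the result.

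**What to change.** Replace the last sentence of Section 7.6 with: *Noncompliance does not remove data from the ITT or safety analyses. It affects PP membership only, under criteria fixed in advance, and each decision and its reason is documented before database lock without reference to outcome data.*

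The criteria still have to be written. Product weight alone will not serve easily, because use is as needed beyond a minimum and over differing areas, so no expected weight is defined.

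Reconcile Sections 6.5.2, 7.6, 9.2 and 12.2. Section 6.5.2 lets some subjects continue for safety evaluation only, at discretion, and the plan should state how their efficacy data enter each analysis set.

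Secondary change, in Section 12.4: add that the planned analysis is always reported, and that any other analysis not specified before database lock is labelled post hoc.

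Cost: a few sentences, plus agreement on the noncompliance criteria. Results may look slightly less favourable.

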8. TREATMENT OF SUBJECTS

8.1 Informed Consent Form

An IRB-approved informed consent form (ICF) will be given to each prospective subject before participation in any study procedures. Prospective subjects will be given as much time as needed to read the ICF and will have the opportunity to have any study-related questions answered to their satisfaction prior to signing the ICF. If further questions exist, prospective subjects will be given sufficient time during the visit to have questions regarding the study and/or the ICF answered by the Investigator or study coordinator prior to signing.

8.2 Subject Identification

Enrolled subjects will be assigned a 3-digit number in conjunction with their initials that will uniquely identify every subject on the study. The numbers will remain with the subject throughout the study and should be used in all references to the individual in this study. No subject number will be reassigned once the study begins.

8.3 Subject Instructions for the Study

Subjects will be provided with the following instruction to follow during the study:

8.3.1. Study Product Usage Instructions:

The study products are used on both face and body:

- *Step 1: Cleanser* – wet skin with lukewarm water, apply the cleanser to wet skin and massage gently. Rinse well and pat dry.
- *Step 2: Moisturizer* – at least twice daily, in the morning and evening, apply the moisturizer liberally to the lesions and all over the body. Reapply the moisturizer as needed throughout the day.
 - If your psoriasis treatment is topical prescription, you can first apply the prescription treatment following its instruction. Wait at least 10 minutes before applying the study moisturizer to the lesions and all over.
- *Step 3: Sunscreen SPF 35* – if you are planning on spending time outdoors, apply the sunscreen to entire face and body before sun exposure once the moisturizers are fully absorbed.

8.3.2. Subject Instructions for Study Visits

- If your appointment time is in the morning (prior to noon), do not apply the study products until after completion of the clinic visit. If your appointment time is in the afternoon, you may apply the study products in the morning.
- You must show up to the study site with clean skin at every clinic visit.
- Please select clothing that will allow easy access for assessments at the clinic (e.g., loose-fitting clothing, shorts or skirts, rolled-up sleeves, no tights or boots or turtleneck shirts, etc.) depending on the affected areas.
- Bring the study products and daily diary with you to every clinic visit.

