9.1 Visit Examinations

9.1.1. Visit 1 (Screening / Baseline / Day 0)

Screening and Baseline visit can be combined if subject meets eligibility criteria. The following screening assessments will be performed:

- Obtain ICF and HIPAA form prior to conducting any study specific activity.

Note: Prior to beginning of any study related activities, subjects will be informed about the purpose and nature of the study, the expected post-treatment events, and the potential risks involved with the treatments. Once subjects have completed reading, they will be interviewed to ensure their understanding of the aforementioned forms and be given the

opportunity to ask any study related questions. Subjects declining to sign any of the forms will be dismissed from the study.

- Assess eligibility: review inclusion/exclusion criteria. Subjects failing to meet criteria will be dismissed from the study.
- Record the subject's demographic information, medical history, and concomitant medications.
- Female subjects will need to perform UPT to confirm childbearing potential. The test result must be negative for study qualification.

Once the subject is deemed eligible by the Investigator, the following procedures should be completed:

- Randomize the subject based on the predetermined computer-generated randomization.
- Obtain pre-treatment digital photography of psoriasis lesions, as described in Section 10.2.1, if subject consents.
 - For Site 2 only, perform additional photography (macroscopic, capacitance) of the lesions, as described in Section 10.2.2, 10.2.3.
- Perform investigator clinical grading as described in Section 10.1.
- Perform tolerability assessment as described in Section 11.1.
- Perform QoL questionnaire as described in 10.3.1.
- Dispense study products and diary. Instruct subjects on study product application and diary completion. Remind subjects to bring the study products and diary to the next clinic visit.
- Schedule the next follow-up Visit 2 (Week 2 \pm 3 days).

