10. EFFICACY ASSESSMENTS

The methods for collecting effectiveness data are described in this section. To minimize inter-observer variability, every effort should be made to ensure that preferably the same individual who makes the initial baseline assessments completes all corresponding follow-up evaluations.

Prior to participating in the following procedures, clinic personnel will ensure that subjects have clean test areas and have not applied any topical products. Subjects will acclimate to ambient conditions within the clinic with test areas exposed for at least 15 minutes. The designated rooms will be maintained at a temperature of 68-75 °F and the relative humidity will range from 35%-65%.

[figure not shown]
The methods for collecting efficacy data are:

- Clinical Grading by Investigator
- Lesion Photography
- Subject Questionnaire

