10.2.2. Macroscopic Imaging

Macroscopic imaging procedure will be performed using Visioscan® VC 20plus at Baseline, Week 2, 4, and 8, at Site 2 only. Images will be taken of each subject's lesion at the same location.

Prior to imaging procedures, clinic personnel will ensure that subjects have clean skin on the lesion area as described in the study procedures. Subjects will be carefully positioned for each photography.

Visioscan® VC 20plus (Courage + Khazaka electronic GmbH, Koln, Germany) is a UVA-light video camera with high resolution to study the skin surface directly. The image shows the structure of the skin and the level of skin texture. The imaging area is 10 mm x 8 mm displayed in 255 pixels. The Visioscan software will be used to calculate the analyze the images for skin roughness and smoothness. Images can be displayed in 2D and 3D format.

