10.2.3. Capacitance Imaging

Capacitance imaging procedure will be performed using MoistureMap MM 200 at Baseline, Week 2, 4, and 8, at Site 2 only. Images will be taken of each subject's lesion at the same location.

Prior to imaging procedures, clinic personnel will ensure that subjects have clean skin on the lesion area as described in the study procedures. Subjects will be carefully positioned for each photography.

MoistureMap MM 200 (Courage + Khazaka electronic GmbH, Koln, Germany) features a sensor based on capacitive-touch imaging technology with hardened surface. The sensor gives graphical information on the near surface hydration distribution and the micro-topography of skin and other tissue which are quantitatively assessed. The imaging area is 1.8 mm x 1.28 mm displayed on a scale of 255-pixel level, showing evenness of hydration distribution.

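### Section 8.3.2 permits study product on the morning of an afternoon visit, Section 10 requires that no topical has been applied, and any residue left on the skin could be measured at follow-up but not at Baseline.

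*Combined protocol and SAP*

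**What the plan says.** Section 8.3.2 sets two visit-day rules. Subjects with a morning appointment are told "do not apply the study products until after completion of the clinic visit". For the others it says: "If your appointment time is in the afternoon, you may apply the study products in the morning". A further bullet applies to everyone: "You must show up to the study site with clean skin at every clinic visit".

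Section 8.3.1 describes the morning application: "at least twice daily, in the morning and evening, apply the moisturizer liberally to the lesions and all over the body". The product therefore goes on the lesions that are graded and imaged.

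Section 10 sets the condition for the efficacy procedures: "clinic personnel will ensure that subjects have clean test areas and have not applied any topical products". It adds at least 15 minutes of acclimation with the test areas exposed. For the Site 2 imaging, Sections 10.2.2 and 10.2.3 repeat that "clinic personnel will ensure that subjects have clean skin on the lesion area as described in the study procedures".

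In Section 9.1.1, products are handed out at the end of Visit 1, after photography, grading and tolerability: "Dispense study products and diary. Instruct subjects on study product application and diary completion". Section 12.4 tests mean change from Baseline against zero, with no control group.

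**The concern.** The two instructions cannot both be followed by an afternoon subject who applies moisturizer that morning. The site must either assess over product or turn away a subject who did as told. Nothing says which, and the two sites may decide differently.

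If the assessment goes ahead, the imbalance is one-sided in time: follow-ups can carry study product and Baseline cannot. A cream made largely of glycerin, petrolatum and dimethicone (Appendix I) can plausibly flatten scale and soften roughness for some hours. Change from Baseline would then mix a visit-day film with the 2- to 8-week effect the trial is meant to describe. With no control group, nothing cancels it.

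The outcomes most open to this are the scaling component of TLSS, investigator dryness (graded as roughness in Section 11.1) and macroscopic smoothness and roughness. Capacitance imaging is also open to it, because "The sensor gives graphical information on the near surface hydration distribution". BSA and induration are much less exposed.

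**Working it through.** **Can the texts be reconciled as they stand?**

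1. Section 8.3.2 allows product on the morning of an afternoon visit. Section 10 asks staff to ensure that none has been applied. Section 10 gives no time window that would let a morning application count as not applied.
2. Clean skin is required in Sections 8.3.2, 10, 10.2.2 and 10.2.3. None of them defines it, gives a product-free interval, describes washing at the clinic, or says what to do when product was used that morning. In Section 10, having applied no topical is a separate condition alongside cleanliness. Acclimation is not described as a removal step.
3. Dryness is graded under Section 11.1, which sets no visit-day product condition of its own.
4. The Section 10 wording covers all topicals. Section 8.3.1 lets subjects on a topical prescription apply it before the moisturizer, and the morning-visit restriction in Section 8.3.2 names only study products. Same-day prescription use is therefore also unresolved.
5. Section 7.6 has a daily diary of applications, but does not say that it captures clock time or that the analysis uses it.

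**How large could the effect be?** The documents give no effect size, SD or power figure, so there is nothing to reproduce. What follows is an illustration.

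From the documents: n = 40, the minimum number of completers (Section 6.1); one-sample t-test of change from Baseline (Table 5); 5% two-sided (Section 12.1), hence 2.5% in the favourable direction.

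Assumed: no change other than residue; SD of TLSS change s = 2.5; residue lowers TLSS by e = 1 or 2 of 24 points; a share f of subjects is affected.

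Formulas:

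- mean shift m = f × e
- SD of the mixture S = √(s² + f(1 − f)e²)
- noncentrality δ = m√n / S
- chance of a false significant decrease = P(T > 2.023), with T noncentral t on 39 degrees of freedom

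Example, f = 0.5 and e = 2: m = 1.0; S = √(6.25 + 0.25 × 4) = √7.25 = 2.693; δ = 1.0 × 6.325 / 2.693 = 2.349; probability 63.0%.

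| Share f | Residue e | m | S | δ | Probability |
|---|---|---|---|---|---|
| 10% | 1 | 0.10 | 2.518 | 0.251 | 4.3% |
| 10% | 2 | 0.20 | 2.571 | 0.492 | 6.9% |
| 25% | 1 | 0.25 | 2.537 | 0.623 | 8.8% |
| 25% | 2 | 0.50 | 2.646 | 1.195 | 21.4% |
| 50% | 1 | 0.50 | 2.550 | 1.240 | 22.7% |
| 50% | 2 | 1.00 | 2.693 | 2.349 | 63.0% |

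With a larger assumed SD of 4, the 50% rows fall to 11.6% and 32.1%. If every session had the same product-free state as Baseline, m would be zero and the rate would return to 2.5%.

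**The case against.** The strongest reply is that the plan already contains the safeguard. Section 10 makes staff responsible for the check, subjects must arrive with clean skin, and the imaging sections repeat this. Bias needs the permission to be used, the product to remain on the skin, and the check to lapse. This stands, and it limits the claim to what can happen. It does not remove the conflict: if Section 10 is enforced, the Section 8.3.2 permission cannot be used.

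Three stronger readings are tempting, and the documents support none of them.

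- *A reader might infer that residue will be recorded as improvement, always in the product's favour.* The documents do not show that the check fails. Nor do they show which way a film moves capacitance homogeneity; an uneven film could lower it.
- *A reader might take the upper TLSS figures as this trial's error rate.* They assume that half the subjects are assessed over product. A 2-point drop confined to scaling would also be a full named grade, still present hours later. In addition, all subjects are on or starting prescription treatment, so zero other change is not a realistic expectation here.
- *A reader might compute a false significant decrease in dryness.* Dryness is a tolerability measure. Section 4.2 and Table 5 need only the absence of a significant increase, so the relevant risk is a masked worsening.

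Baseline, too, is certain to be free only of study product. No washout of the subject's own skincare is stated, so absence of other topicals at Baseline rests on the same Section 10 check.

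**Conclusion.** The contradiction between Sections 8.3.2 and 10 is certain. The bias is conditional and its size is unknown. If the check is not enforced, residue is expected to favour the product on TLSS scaling, dryness and macroscopic smoothness and roughness, and may shift capacitance homogeneity either way. Under the stated assumptions, the chance of a false significant TLSS decrease runs from barely above nominal with a tenth of subjects affected to well above it with half affected. The affected share, the residue and the SD are all assumed. The point is worth correcting before data collection, because application times that were not recorded cannot be recovered later.

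**What to change.** - Reconcile Section 8.3.2 with Section 10 so that one visit-day product state, the same as at Baseline, applies to every grading session (including dryness under Section 11.1) and every imaging session.
- State how same-day use of a topical prescription fits the Section 10 condition, without altering the prescribed treatment.
- Record time since last application on the CRF at each visit.
- Repeat the TLSS, dryness and imaging analyses without visits that had same-day study product, as a supportive sensitivity analysis.

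The cost is a wording change, one CRF field and one extra analysis. The remaining subset is self-selected and may be small at Site 2, where only 20-25 subjects have imaging, so it should be read as supportive only. Booking each subject's visits in the same half of the day would help but is optional.
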